5.3 Informed Consent Procedures

- **Indicate if informed consent will be obtained and/or if you are requesting a waiver of informed consent or waiver of documentation of informed consent. If the research involves multiple phases, specify for which phases of the research the waiver(s) is being requested and/or the informed consent will be sought.**

Approved study team members will obtain informed written consent from all participants in the study.

- **Describe who will be obtaining informed consent, if applicable, and any circumstances that may need to be addressed (e.g. subjects with impaired decision making ability and the use of a legally authorized representative, etc.)**

Approved study team members will obtain informed written consent from all participants in the study. All participants will receive a copy of the informed consent form. Potentially eligible participants will have the study described to them verbally, either in person or over the phone before they are scheduled for any study-related testing sessions. Upon arrival at the first in-person study-related testing session, potential subjects will be provided with a detailed oral explanation of the study by an approved study-personnel. The oral explanation will use statements from the consent form and be performed in the laboratory or in another private room with only the participant and investigators present. Participants will be asked;

“Do you understand what is being asked of you in this study?”

“Do you have any questions regarding this procedure or study?”

Participants will be given the opportunity to ask questions during the consent process. Participants will have the option to have a family member present during the consent process. Individuals who are; not yet adults, cognitively impaired adults, and adults unable to provide informed consent, will not be recruited for this study.

- **If applicable, indicate how local site study personnel will be trained regarding human subjects protections requirements and how to obtain and document informed consent.**

All study personnel will complete CITI training and the Hines VA required TMS training regarding human subjects protections. Prior to administering informed consent all new study personnel will first observe a senior study personnel obtaining informed consent. New personnel will also meet with senior study personnel to review the informed consent process and associated administrative procedures.

5.4 Inclusion/Exclusion Criteria

- **Describe the criteria that determine who will be included in or excluded from the study.**

Inclusion/Exclusion Criteria

Inclusion criteria: a) age 18 to 80 years; b) medically stable with medical clearance from physician to participate; c) neurologic level of the spinal cord injury between C1-T10 with American Spinal Injury Association (ASIA) Impairment Scale (AIS) C or D; d) more than 6 months since initial injury; e) passive range of motion of the legs within functional limits and not restricting the ability to engage in locomotor training; f) able to ambulatory 10 m with no physical assistance, use of assistive devices, such as a single cane or rolling walker, and use of braces that do not cross the knee joint, such as an ankle-foot orthosis, are permitted.

Exclusion criteria: a) excessive spasticity in the lower limbs as measured by a score of > 3 on the Modified Ashworth Scale on all test muscle groups; b) inability to tolerate 30 minutes of standing; c) severe cardiovascular and pulmonary disease; d) history of recurrent fractures or known orthopedic problems in the lower extremities (i.e. heterotopic ossification); e) concomitant central or peripheral neurological injury (i.e. traumatic head injury or peripheral nerve damage in lower limbs); f) inability to provide informed consent due to cognitive impairments; g) presence of unhealed decubiti or other skin compromise; h) enrollment in concurrent physical therapy or research involving locomotor training; i) use of braces/orthotics crossing the knee joint; j) known pregnancy.

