We have conducted the Lane Width Optimization test on 12 ambulatory individuals with chronic iSCI, who met the inclusion/exclusion criteria of the current proposed intervention, to assess feasibility and construct validity. Participants walked at their preferred treadmill speed with their arms free to move throughout the experiment. Participants were instructed to do their best to keep the line representing their COM position within the green target lane. All participants were able to perform the test and the target lane rapidly converged on a width that was challenging for everyone. There were strong and significant ($p < 0.05$) Pearson correlations between the final (narrowest) lane width achieved during the two-minute test and clinical outcome measures recorded from each participant (Pearson correlations of final lane width and the Berg Balance Scale $r = -0.67$; the 10-Meter Walk Test at maximum speed $r = -0.61$; and the Timed Up and Go $r = 0.80$). Thus, a narrower lane width corresponded with higher functional balance, walking speed, and adaptability. **The Lane Width Optimization test shows convergent validity with established clinical measures of dynamic balance and gait function.** This test will provide a quantitative method to assess control of lateral COM motion during walking.

Feasibility of Locomotor Trailing in a Movement Amplification Environment for Individuals with iSCI

We have collected pilot data demonstrating that **locomotor training performed in a movement amplification environment is safe, feasible, and likely effective for improving dynamic balance of ambulatory individuals with iSCI**. Three individuals with chronic iSCI, who met inclusion/exclusion criteria matching the proposed trial, received 16-18 treadmill training sessions in the movement amplification environment. One participant was classified as lower functioning (initial preferred gait speed < 0.5 m/s). All three participants used assistive devices (straight cane, wheelchair) during community ambulation. The goal of each 45-minute training session was to perform as much walking as possible within the movement amplification environment. We aimed to progress the movement amplification gain and treadmill walking speeds within and across sessions. As individuals' ability to walk in the movement amplification

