Participants will be stratified by gait speed (half of the participants will have a preferred over ground gait speed ≥ 0.5 m/s and half of participants will have a preferred over ground gait speed < 0.5 m/s) and then randomized into two locomotor intervention groups:

The **Control group** will receive high intensity locomotor training performed on a treadmill [60].

The **Experimental group** will receive high intensity locomotor training performed on a treadmill in a movement amplification environment created by the Agility Trainer.

We will conduct **clinical outcome measures** to assess changes in functional gait and balance and quality of life. We will conduct quantitative **laboratory assessments** to evaluate changes in dynamic balance and associated gait patterns. Finally, to assess if the effects of locomotor training impact participation in walking activities outside of the laboratory/clinical setting, we will measure daily **steps taken in the home and community**.

To ensure that gait and balance are stable prior to beginning the intervention, we

will measure 10 m walk speed and Berg Balance Scale score during an initial **Screen**. These two measures will be repeated a week later during the Baseline (**BSL**) assessment session to ensure the participant's initial performance is stable. If measures are not stable, measures will be repeated a week later. If measures do not stabilize after three-weeks of testing, the participant will not be enrolled in the training intervention. Clinical outcome measures and laboratory assessments will be performed at four time points (**BSL**, **Mid**, **Post**, and **Follow Up**) encompassing the 20-session training intervention (Figure 7). Average number of steps taken in the home and community environment will be estimated from data recorded during 1-week periods occurring at three time points corresponding with **BSL**, **Post**, and at the 3-month **Follow Up**. (Figure 7).

Figure 7. Timeline of the 22 to 26 week schedule for assessments and locomotor training intervention. The length of each individual study segment is indicated.

Daily Steps Assessment	Training Intervention	Training Intervention	Daily Steps Assessment	Daily Steps Assessment
Screen 1-Day	Stepping 1-week	BSL 1-Day	Sessions 1-10 3-5 Weeks	Mid 1-Day
Screen, Consent, 10 MWT, BBS	Clinical And Laboratory Assessments		Clinical And Laboratory Assessments	Clinical And Laboratory Assessments

Locomotor Training Interventions

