5.2 Recruitment Methods

- **State how many subjects will be needed.**

We will enroll 46 participants with iSCI in the study.

- **Describe when, where, how and by whom potential subjects will be identified and recruited.**

We will enroll 46 participants with iSCI in the study. Veterans will be recruited from the Spinal Cord Injury Service at Edward Hines Jr. VA Hospital. During the last three years the Hines Spinal Cord Injury Service treated 553 unique patients with SCI. We will work with a highly experienced clinical coordinator at the Edward Hines Jr. VA Hospital to recruit participants from this facility. [name] has established a strong professional relationship with the clinical staff from the Spinal Cord Injury Service to identify, contact, and screen potential study participants. [name] has been involved with multiple SCI related studies in the past, including studies run by the PI of the proposed study. Her familiarity working with the target study population and their clinical providers will be an asset to the proposal. We anticipate that the pool of eligible participants available through the Edward Hines Jr. VA Hospital may not be sufficient to meet our full enrollment objective.

As needed, additional Veteran and non-Veteran participants will be recruited through the Shirley Ryan AbilityLab. The Shirley Ryan AbilityLab maintains the *Clinical Neuroscience Research Registry* a database of interested, potential study volunteers with SCI. The Registry is populated through referrals from associated inpatient and outpatient physical therapy clinics of the Shirley Ryan AbilityLab and through postings at clinics, support groups, and SCI organizations. The volunteer database currently has 475 volunteers with up-to-date-contact information. Of these volunteers greater than 215 individuals identify that they are able to walk in therapy, home or the community. Individuals registered in the database have consented to allowing researchers to contact them directly to discuss opportunities to participate in ongoing research projects. [name], a co-Investigator on this proposal, jointly oversees the maintenance and population of the volunteer database. She will ensure that the study team receives access to the database. In addition, the Shirley Ryan AbilityLab treats ~140 SCI inpatients and 225 SCI

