5.6 Data Analysis

- Provide sample size determination and analysis (include anticipated rate of screen failures, study discontinuations, lost to follow-up etc.).**

Our primary measure to assess dynamic balance during walking is the Lane Width Optimization Test. The test challenges participants to maintain their medio-lateral COM position within a target lane during treadmill walking. If successful, the difficulty of the task becomes progressively more difficult by continually narrowing the width of the target lane until the participant is unable to maintain the target position. The lateral COM excursion per stride during the narrowest lane width achieved **provides a quantitative measure of dynamic balance during gait**. A reduction in the minimum lateral COM excursion following training would indicate improved dynamic balance during gait.

We performed a power analysis to determine the minimum sample size required to detect significant changes in dynamic balance using the lane width optimization test. To estimate the population variability, we used data from 13 individuals with iSCI, having similar characteristics to the target population, performing unassisted treadmill walking [102]. We found that typical lateral COM excursion per stride during preferred speed treadmill walking was 0.083 ± 0.014 m (mean \pm standard deviation). To estimate effect size, we used pre- and post-intervention data from three individuals with iSCI who received 16-18 high intensity locomotor training sessions performed in the movement amplification environment. Following the intervention, these individuals improved dynamic balance (decreased their lateral COM motion excursion during walking) by 32-36%. To detect a 20% difference in improvements in dynamic balance between training groups we will need a sample size of 7 individuals per group at $\alpha = 0.05$ and a power of 80%. We plan to enroll 46 individuals. A recent locomotor training intervention using individuals with iSCI, conducted by one of our study team members at a nearby facility, lost 12% of their participants to drop out [60]. With a conservative estimate that we will lose 20% of participants to drop out, an initial enrollment of 46 individuals would yield 14 high functioning and 14 low functioning participants (stratified based on the gait speed). This number, double that estimated by the power analysis, should be sufficient to assess training effects on dynamic balance.

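### Eligibility does not exclude people already trained in the movement amplification environment, so the three pilot participants could be randomised

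*Combined protocol and SAP*

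**What the plan says.** Exclusion (h) in section 5.4 reads "enrollment in concurrent physical therapy or research involving locomotor training". It is the only criterion that concerns other training. The time criterion, "more than 6 months since initial injury", dates the injury and not the last course of therapy.

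The feasibility part of section 2.0 reports: "Three individuals with chronic iSCI, who met inclusion/exclusion criteria matching the proposed trial, received 16-18 treadmill training sessions in the movement amplification environment". Section 5.6 uses these three people's pre- and post-training data to estimate the effect size. It reports improvements of 32-36% and then plans for a 20% difference between arms.

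Section 5.1 has one pre-enrolment safeguard. The 10 m walk speed and Berg Balance Scale are measured at Screen and repeated a week later at BSL. "If measures do not stabilize after three-weeks of testing, the participant will not be enrolled in the training intervention". No numerical threshold for stability is given.

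On recording and adjustment:
- The history items in section 5.5 do not include earlier gait or locomotor training. Section 5.1 has only a general medical history entry.
- Stratification in section 5.1 is by gait speed alone.
- The covariates named in section 5.6 are initial walking speed, severity and location of injury, spasticity and age, given as examples.

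**The concern.** Read literally, section 5.4 admits a person who has completed nearly a full course of the experimental training, since the pilot's 16-18 sessions compare with 20 in the trial. Such a person may carry part of the Experimental effect in the BSL value and have little left to gain. In the Experimental arm this pulls the observed gain down. In the Control arm it places someone trained in the amplification field in the comparison group and pulls the Control gain down.

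If the pilot participants enrolled, the hypothesis would also be tested partly on the people whose results supplied the effect estimate, so trial and pilot would not be independent evidence. Because earlier training is not a listed item, the analyst could not count on having the data to adjust for it or to run a sensitivity analysis.

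**Working it through.** The plan states no figure on this point. The check has two parts: what the text allows, and how much it could matter.

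**Text.** Each place that could catch a pilot participant fails to do so.
- Exclusion (h) does not apply, because the pilot training has ended.
- The stability check looks for change over one to three weeks, so a gain that has plateaued passes. It also leaves out the primary measure, lateral COM excursion in the Lane Width Optimization Test. Section 5.1 itself says the Berg scale does not assess dynamic balance and has a ceiling in higher functioning people.
- History, stratification and named covariates do not mention earlier training.

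**Inputs (section 5.6).** Mean lateral COM excursion 0.083 m, SD 0.014 m, from 13 people at preferred speed; pilot gain 32-36%; planned difference D = 20%, or 0.20 × 0.083 = 0.0166 m if taken on that mean; enrolment 46, so 23 per arm.

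**Assumptions, not in the documents.** All three pilot participants enrol and gain nothing further. Other Experimental participants gain E = 32-36%, as in the pilot, so the Control gain is C = E − 20 = 12-16%. Allocation is simple 23:23, ignoring the speed strata.

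**Effect on the contrast.** With a of the three in Experimental and 3 − a in Control:

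observed difference = D − (a/23)E + ((3 − a)/23)C

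probability = C(23,a) × C(23,3−a) / C(46,3), where C(46,3) = 15,180

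| a in Experimental | Probability | E = 32, C = 12 | E = 36, C = 16 |
|---|---|---|---|
| 3 | 1,771/15,180 = 0.117 | 20 − 4.17 = 15.8% | 20 − 4.70 = 15.3% |
| 2 | 5,819/15,180 = 0.383 | 20 − 2.78 + 0.52 = 17.7% | 20 − 3.13 + 0.70 = 17.6% |
| 1 | 0.383 | 20 − 1.39 + 1.04 = 19.7% | 20 − 1.57 + 1.39 = 19.8% |
| 0 | 0.117 | 20 + 1.57 = 21.6% | 20 + 2.09 = 22.1% |

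The average over allocations is D(1 − 3/46) = 18.7%. All three share an arm with probability 2 × 0.117 = 0.23. If the Control arm were assumed to gain nothing (E = D = 20%), the a = 3 row would be 20 × (1 − 3/23) = 17.4%.

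**Baseline imbalance.** If all three fall in one arm, started near the quoted mean and kept their full gain, that arm's BSL mean shifts by 3 × 0.083 × 0.32/23 = 0.0035 m to 3 × 0.083 × 0.36/23 = 0.0039 m. This is 21-23% of 0.0166 m.

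**Power.** Two-sided two-sample t-test, SD 0.014 m, difference (1 − f) × 0.0166 m, where f is the share with no further gain:

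| f | 14 per arm | 18 per arm |
|---|---|---|
| 0 | 0.86 | 0.93 |
| 3/46 | 0.81 | 0.90 |

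Fourteen per arm follows from the 28 completers in section 5.6 if split evenly; 18 follows from 46 × 0.8 = 36.8. These values show relative loss only. With the same inputs this test needs 13 per group, not the plan's 7, which appears only with an added assumption such as change scores with a pre-post correlation of 0.7.

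**The case against.** The strongest reply is that earlier training is fixed before randomisation, so it is balanced between arms in expectation. The section 5.6 model works with change across assessments, so a stable retained gain is simply a baseline level, apart from headroom. The covariate list is open-ended. Even with all three enrolled, power in the illustration stays at or above 80%. All of this stands, and it limits the point to dilution, distortion by chance and lost independence from the pilot. The open covariate list helps only if prior training is recorded.

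The documents do not say that the pilot participants will be approached, and the text reviewed does not say how long their gains lasted. That also stands. The point is that the rule permits their entry.

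A reader might infer several stronger things that the documents do not support:
- *That the effect estimate would be biased, always towards zero.* It would not. A plateaued person in Control widens the contrast, as the last row of the first table shows.
- *That repeat volunteers are likely.* The section 5.2 sentence that the coordinator "has been involved with multiple SCI related studies in the past, including studies run by the PI of the proposed study" describes staff experience and says nothing about participants returning.
- *That former participants of the earlier high-intensity trial are a comparable problem.* Section 5.6 describes it as "A recent locomotor training intervention using individuals with iSCI, conducted by one of our study team members at a nearby facility". Its cited report is dated 2017, and it did not use movement amplification.
- *That a washout for ordinary gait therapy is required, for instance the trial's own 3-month interval to Follow Up.* That interval is used to assess outcomes after training, and nothing shows that effects have gone by then. The stability check already screens out people whose 10 m speed or Berg score is still changing. Admitting previously treated people with chronic injury is a defensible choice.

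**Conclusion.** The gap is real but narrow. Section 5.4 as written admits people who have already had the experimental training, and nothing later in the plan detects them or ensures that they can be adjusted for. Only three such people are identified.

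If all three enrolled and gained nothing further, the expected difference falls from 20% to 18.7%. The range by allocation is about 15% to 22%, and the chance of all three in one arm is about 0.23. These figures rest on unstated re-enrolment and on a worst-case assumption about further gain. The arm gains are inferred from the pilot, and the baseline shift also assumes full retention and uses a mean from preferred-speed walking instead of the primary test. The documents do not support a claim of systematic bias or of a large loss of power. The case for changing the plan is that the problem is avoidable at almost no cost.

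**What to change.** 1. Add to the exclusions in section 5.4: any previous training in the movement amplification environment, including the pilot series.
2. Add to the Screen history in section 5.5: prior physical therapy or research involving locomotor training, with its end date.
3. State in section 5.6 that this variable will be used as a covariate or in a sensitivity analysis, and specify which before outcome data are examined.

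Whether to require an interval since ordinary gait therapy, and how long, is a recruitment trade-off for the sponsor to decide and justify.

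The cost is a short amendment, one screening question and about three fewer candidates, against more than 215 registry volunteers who report being able to walk (section 5.2).

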5.5 Study Evaluations

- **Describe all evaluations to be conducted (including screening; tests/questionnaires that will be administered; any procedures that subjects will be required to complete) and data collection methods. Include materials as an appendix or separate attachment.**

The following data will be recorded directly from participants.

Demographic and Medical History

After providing written informed consent, all potential participants will undergo a screening for inclusion and exclusion criteria. We will then collect demographic information and a brief medical history from participants who meet all inclusion and exclusion criteria. The information collected will include; age, gender, date of SCI, level of injury, cause of injury, current medications, current ambulatory ability in the home and community, use of any assistive devices, and self-reported falls in the past year.

Clinical Outcome Measures

Clinical Outcome measures will be performed by a clinician at four time points during the intervention. We will collect data using measures that span each level of the International Classification of Function, Disability, and Health (ICF) (body structure and function, activity, and participation), utilizing a combination of performance based and self-report measures. The measures we will use include: the Lower Extremity Motor Score (LEMS) portion of the International Standards for Neurological Classification of Spinal Cord Injury (ISNCSCI), manual muscle tests of hip abductor strength, the Walking Index for Spinal Cord Injury (WISCI II), the Functional Gait Assessment (FGA), the 10 meter walk test (10MWT), the Activities-Specific Balance Confidence scale (ABC), the reactive balance test items from the Balance Evaluations Systems Test (BESTest), the Berg Balance Scale (BBS), the World Health Organization Quality of Life scale (WHOQOL-BREF) and the International Consultation on Incontinence Questionnaire-Urinary Incontinence Short Form (ICIQ- UI SF).

Laboratory Assessments

Laboratory Assessments of dynamic balance during walking will be made at four time points during the intervention. Specifically, we will collect kinematic data as participants perform treadmill walking. To assess COM and stepping kinematics we will record 3D coordinates of 40 reflective markers placed on the trunk, pelvis and lower limbs using a 12-camera motion capture system (Qualisys, Gothenburg Sweden).

Stepping Activity in the Home and Community

We will assess the amount of daily stepping in the home and community during three one-week periods. Daily stepping will be measured and recorded using a StepWatch4 (Modus, Edmonds, WA) activity monitor. The device has a battery life of 35 days and will record individual stepping data on the resolution of seconds. During each assessment period, the microprocessor-based accelerometer will be worn around the ankle during all waking hours (except bathing). Our primary measure of daily stepping will be the total number of steps taken per day averaged across each assessment period. Secondary measures used to quantify changes in activity level include; the number of minutes of the day with at least one step, and percent of a 24-hour day with no walking.

Performance during Individual Locomotor Training Sessions

We will collect data from participants to document the details of every locomotor training session. The data we will collect include; vital signs before, during and after training, exertion and workload - monitored via heart rate and the 6-20 point RPE scale monitored throughout the training session, and number of steps taken during the training session.

Participant perception of training effects

We will assess the perceived changes of participants following high intensity locomotor training in both training and control group to understand the effects of our training intervention. This semi-structured interview will have open ended questions and predetermined prompts used to determine the subjective impact of our training intervention on participants perceived balance confidence, walking capacity, everyday life and other changes that were noted as following participation in this intervention. This interview will be performed 3 months after training is completed. During the interview, questions will be asked by a researcher not involved in training interventions. The interview will take about 15 to 30 minutes. Interview performed will be audio recorded and transcribed by our researchers.

